8.2.4. Efficacy analysis

8.2.4.1. Clinical efficacy

Response rate (number of effective patients / [number of effective patients + number of ineffective patients]) and its 95% confidence interval will be calculated.

8.2.4.2. Pain score

Summary statistics specified in Section 8.1.1 will be calculated for the pain score and its change from baseline at each time point, and test will be performed for comparison between before and after administration of Lyrica. Patients whose pain score at Week 13 LOCF decreased by at least 30% or at least 50% from baseline are defined as 30% or 50% responders, respectively. Then, number and proportion of responders will be calculated.

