## 2 Study population

The survey covers the patients satisfying all of the following requirements:

- Patients not participating in any other survey or study of the product
- Patients having never used the product before the survey

The indications, dosage and administration of the product are specified below:

Indications: Neuropathic pain\*, pain associated with fibromyalgia\*\*

[Neuropathic pain]

Dosage and Administration: The usual starting dose in adults is 150 mg/day of pregabalin orally administered in 2 divided doses, which may be gradually increased to 300 mg/day over one week or longer. The dose may be adjusted depending on age and symptoms as appropriate, provided the daily dose may not exceed 600 mg and the product should be orally administered in 2 divided doses regardless of the daily dose.

The latest version of the package insert should be referred to when the product is prescribed.

\* Neuropathic pain to be enrolled in April 2013 and thereafter will cover peripheral neuropathic pain including trigeminal neuralgia, peripheral entrapment neuropathy, iatrogenic neuropathy, neuropathy due to tumor-induced nerve compression or infiltration, posttraumatic pain, and chronic cauda equina syndrome, as well as central neuropathic pain.

\*\* The survey does not cover pain associated with fibromyalgia.

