## 5.4 Observation period

The observation period will start on the first day of treatment with the product (Day 1) and last until Week 13 (Day 91). However, in cases where treatment has been completed or discontinued before Week 13, observation will be continued until completion (discontinuation) of treatment, and follow-up will be made for one week (7 days) after completion (discontinuation) of treatment. During this survey, safety will be evaluated on the day of the first visit after the end of the observation period (including the last day of the observation period), as a rule. In cases where treatment has been completed or discontinued, safety will be evaluated until the day of the first visit following 7-day period after the completion (discontinuation) of treatment, and safety information will be collected for this period.

**Supplementary note:** Completion of treatment means cases where further treatment with the product is judged unnecessary because of achievement of the purpose of treatment set at the start of treatment (e.g., cure of target diseases).

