## 6.5 Clinical evaluation

**(1) Patient-rated pain score**

Before the start of treatment (including the first day of treatment) and at Week 4 and Week 13, the pain experienced during the past 24 hours will be rated at the time of getting up in the morning on a 11-grade scale, ranging from 0 (no pain) to 10 (the most severe pain possible). In cases where treatment has been completed or discontinued before Week 13, the data at the time of completion (discontinuation) of treatment will be entered.

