## 6.6 Patient summary

The appropriateness of continuation of treatment with the product will be checked on the day of safety evaluation. In cases where continuation of treatment with the product is not possible, one major reason should be selected from the alternatives given below. If adverse events, abnormalities in laboratory parameters or the death of patient is selected as a major reason, the relevant data should be entered in the "adverse event" field.

- [1] Insufficient clinical efficacy
- [2] Recovery (effective)
- [3] Adverse events
- [4] Abnormalities in laboratory parameters
- [5] Death of patient
- [6] Lost to follow-up
- [7] Others

In cases where no revisit has been made after the start of treatment, it should be entered in the "Confirmation of revisit after the start of treatment" field.

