6.4. Covariates

For safety and efficacy of Lyrica, no covariates or potential covariates are identified from clinical study data, etc. obtained to date.

7. Handling of missing data

If the seriousness/outcome of adverse events and action taken with Lyrica for the adverse events are missing, they will be handled as “unknown” at tabulation.

If body weight is not measured within the acceptable range at each time point (Appendix 1), it will be handled as missing and will not be imputed.

If there is no data of pain score and sleep interference score, it will be handled as missing and will not be imputed in “Week 4” and “Week 13” assessments. If data is missing at Week 13, it will be imputed with the data obtained at the last time point post-dose in “Week 13 LOCF” assessment.

8. Statistical methods and statistical analyses

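### The 30% and 50% pain responder rates are planned only at Week 13 LOCF, so patients who stop early for reasons other than recovery can count as responders, and no planned table shows how many

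*SAP*

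**What the plan says.** SAP 8.2.4.2 plans summary statistics for the pain score at each time point. It then adds one responder definition: "Patients whose pain score at Week 13 LOCF decreased by at least 30% or at least 50% from baseline are defined as" responders at that threshold, followed by their number and proportion. SAP 8.2.4.7 repeats this by target disease, for diseases with about 100 patients or more.

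SAP 7 keeps unimputed Week 4 and Week 13 assessments beside a Week 13 LOCF assessment. In the LOCF assessment, if Week 13 is missing, "it will be imputed with the data obtained at the last time point post-dose". No condition is placed on why the score is missing. For patients who finish or stop before Week 13, protocol 6.5 says that "the data at the time of completion (discontinuation) of treatment will be entered".

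The protocol separates success from other stops. In section 5.4, "Completion of treatment means cases where further treatment with the product is judged unnecessary because of achievement of the purpose of treatment". In section 6.6, when treatment cannot continue, "one major reason should be selected from the alternatives given below". That list has seven entries: insufficient efficacy, recovery, adverse events, laboratory abnormalities, death, loss to follow-up and others. Only recovery denotes treatment success.

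SAP 8.2.1 tabulates discontinuations by timing in the safety analysis set and, separately, by reason. Neither table is crossed with pain response.

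**The concern.** A proportion of responders at Week 13 is naturally read as the share of patients whose pain was down by 30% or 50% after 13 weeks of use. Under the planned rule it also includes patients who left treatment because of an adverse event, or who did not return, provided the last recorded score was low enough. For a patient lost after the Week 4 assessment, a Week 4 score would stand in for a value nine weeks later.

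The survey has one arm and no comparator, so nothing in the design offsets this, and the percentage will be taken at face value. A reader of the planned tables could not separate sustained responders from patients who stopped for another reason with a low last score.

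**Working it through.** **Is there a figure in the plan to reproduce?** No. The documents give no expected responder rate, no expected share of early stops and no size for the efficacy analysis set. The sizing figures concern adverse reactions. They reproduce (1 − 0.999^3400 = 0.967 against 97%; 3400 × 0.067 = 227.8 against 227) but do not bear on this point.

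**Can a non-recovery stop become a responder?** There are two routes.
1. The Week 13 score is missing, and SAP 7 fills it with the last post-dose score for any reason of stopping.
2. The score at the stop is recorded under protocol 6.5. The schedule in protocol 6 has one column that serves both Week 13 and an earlier completion or discontinuation, so this score may itself sit in the Week 13 field.

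By either route, only the size of the fall decides responder status.

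**Does another planned output show the effect?**
- The unimputed Week 13 assessment is summarised as a score and a change, not as a responder rate. Because of the shared column it may include early-stop scores. The visit windows in SAP Appendix 1 cover laboratory tests and body weight only, so they do not sort this out. An observed-case responder rate at Week 13 would therefore not settle the matter by itself; the split has to use the stop date and reason.
- Adding the non-recovery rows of the by-reason table gives an upper limit on the number affected. It is approximate: the table is not crossed with timing, which includes a category beyond 13 weeks, and it does not say who had a qualifying score.
- The listings in SAP 9 include pain scores and administration records, so the count could be derived, but no table reports it.

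**Size, for illustration.** Let s be the share of the denominator who stop before Week 13 for a non-recovery reason, r the share of those whose last score qualifies, and p the response rate among everyone else.
- LOCF rate = (1 − s) × p + s × r
- Rate with these stops counted as non-responders = (1 − s) × p
- Gap = s × r, whatever p is

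All values of s, r and p are assumed. Gap in percentage points:

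| s | r = 10% | r = 30% | r = 50% |
|---|---|---|---|
| 10% | 1 | 3 | 5 |
| 20% | 2 | 6 | 10 |
| 30% | 3 | 9 | 15 |
| 40% | 4 | 12 | 20 |

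With s = 20%, r = 30% and p = 60%, the LOCF rate is 0.80 × 0.60 + 0.20 × 0.30 = 54.0% and the companion rate is 48.0%. If the denominator were as large as the overall target of 3400, 6 points would be 204 patients.

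For scale, the 95% half-width at a rate of 50% is 1.96 × √(0.25/3400) = 1.7 points with 3400 patients, and 9.8 points with 100, the approximate minimum for the by-disease tables. In the whole set most of the assumed gaps exceed sampling error; in a disease group of 100 most do not.

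**The case against.** The strongest reply is that this is not an error. Scoring patients at Week 13 or at the end of treatment is a legitimate definition and matches how the protocol collects every efficacy measure. The responder rates are descriptive, and the primary efficacy item is the clinical response rate (protocol 7.2.2). Testing is exploratory and there is no decision rule (SAP 4.1, 4.2). Patients with no adverse event information because they never returned are already outside the safety analysis set, and so outside the efficacy analysis set (SAP 5.1, 5.2). Unimputed mean scores, stops by reason and individual listings are planned. Counting every non-recovery stop as a failure is one convention among several.

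Most of this stands, and it keeps the point small. It does not remove it: none of these outputs says how many responders stopped for another reason, and the permission in SAP 8.2.4.7 for further analyses is not a plan to show it.

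Two stronger readings are tempting, and the documents support neither.
- A reader might infer that the LOCF rate is inflated. Measured against sustained response, upward bias is plausible, but no document gives its size. LOCF can also lie below the rate in patients who stay: in the example above it is 54% against 60% among the others.
- A reader might infer that the primary response rate is overstated too, because SAP 8.2.4.1 divides only by patients rated effective or ineffective. Protocol 7.1 limits the efficacy set to patients whose efficacy was appropriately evaluated, while SAP 5.2 removes only those with no efficacy evaluation at all or a non-target disease. Both refer to details set out elsewhere and not available here, so unjudged patients may already be excluded.

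**Conclusion.** The point holds as a minor gap in reporting. As written, the 30% and 50% responder rates can include patients who stopped early for reasons other than recovery, and the planned tables give only an approximate upper limit on their number. The data needed to show the number are collected.

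The size is unknown. The 6-point example and the range of 1 to 20 points rest entirely on assumed stop and response shares and show only that the gap could be trivial or material. The direction follows from the definition: counting these patients as non-responders can lower the rate or leave it unchanged, never raise it. That does not establish that the planned LOCF rate is wrong.

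**What to change.** In SAP 8.2.4.2, keep the Week 13 LOCF responder rates. Add, on the same denominator, a 30% and a 50% rate labelled as a sensitivity analysis. In these, patients who stopped before Week 13 (judged from the dosing period) for any major reason other than recovery are non-responders, and all others keep their LOCF status. Show the number reclassified by reason for stopping.

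The inputs (dosing period, major reason and pain scores) are already collected. The cost is a few table rows and a conservative, less favourable figure beside the planned one. Because treating loss to follow-up and other reasons as non-response is a convention, the new rate should remain a companion and not replace the LOCF rate.

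Optionally, check the separate inclusion criteria for the efficacy analysis set. If patients whose efficacy could not be judged remain in it, report their number and the recorded reasons beside the response rate in SAP 8.2.4.1. If they are excluded, nothing is needed there.

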8.2.4.3. Sleep interference score

Summary statistics specified in Section 8.1.1 will be calculated for the sleep interference score and its change from baseline at each time point, and test will be performed for comparison between before and after administration of Lyrica.

8.2.4.4. PGIC

Number and proportion of patients will be calculated for each of 7-point scale.

8.2.4.5. CGIC

Number and proportion of patients will be calculated for each of 7-point scale.

8.2.4.6. Subgroup analysis

Subgroup analysis of the response rate of clinical efficacy will be performed for each factor specified in Section 5.4. Tests specified in Section 8.1.3 will be performed to evaluate the relationship between patient demographics, etc. and clinical efficacy. Furthermore, test based on the analysis of covariance model specified in Section 8.1.1 will be performed to evaluate the relationship between patient demographics, etc. and change in pain score at Week 13 (or at administration/discontinuation).

In addition, patient demographics, etc. (including breakdown of past medical history and complications, prior and concomitant medications) in each subgroup will be tabulated as necessary for factors showing a significant difference by testing to evaluate the relationship between patient demographics, etc. and efficacy.

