#### 7.2.2 Efficacy analysis

In the efficacy analysis set, the response rate will be set as a primary analysis item. As needed, explorative analysis of factors affecting the efficacy will be also carried out.

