6.2. Efficacy endpoints

- Clinical efficacy: Efficacy of Lyrica at Week 13 will be assessed relative to baseline (including the day of start of treatment).
- Pain score: Patients are asked to rate their pain in the last 24 hours at the time of awakening on an 11-point scale from 0 (no pain) to 10 (worst possible pain).
- Sleep interference score: Patients are asked to rate their intensity of sleep interference in the last 24 hours at the time of awakening on an 11-point scale from 0 (pain does not interfere with sleep) to 10 (pain completely interferes with sleep [could not sleep because of pain]).
- Patients' global impression of change (PGIC): Patients are asked to rate their impression relative to baseline on a 7-point scale from 1 (greatly improved) to 7 (greatly worsened).
1 = greatly improved, 2 = improved, 3 = slightly improved, 4 = unchanged
5 = slightly worsened, 6 = worsened, 7 = greatly worsened
- Clinical global impression of change (CGIC): Investigators rate their impression relative to baseline on a 7-point scale from 1 (greatly improved) to 7 (greatly worsened).
1 = greatly improved, 2 = improved, 3 = slightly improved, 4 = unchanged
5 = slightly worsened, 6 = worsened, 7 = greatly worsened

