8.1. Statistical methods

8.1.1. Analysis of continuous data

Summary statistics (number of patients, mean, standard deviation, median, maximum, and minimum) will be calculated.

If a test is performed for comparison of before and after administration of Lyrica, a paired t-test will be used. If changes before and after administration of Lyrica (change = value after administration - value before administration) are compared between subgroups, the effect of the factor will be tested (P-value will be calculated) with an analysis of covariance model using the factor to be evaluated as a factor and the value before administration as a covariate, and the least squares mean, standard error, and 95% confidence interval of change will be calculated for each subgroup.

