8.1.3. Analysis of binary data

Frequency and its proportion will be calculated. If the confidence interval of proportion is calculated, a 2-sided 95% confidence interval (exact method) will be calculated.

If the proportion is compared between subgroups, Fisher’s exact test and Cochran-Armitage test (exact method) will be performed for the relationships with nominal scale data and ordinal scale data, respectively, and the risk ratio and risk difference with their 95% confidence intervals will be calculated.

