8.2.2. Patient demographics and treatment history

- **Patient demographics**

The following patient demographics will be tabulated in the safety analysis set and efficacy analysis set in accordance with Section 8.1.

- Sex [male, female]

- Age at the start of treatment (continuous data)
- Age category at the start of treatment [<15 years, ≥ 15 to <65 years, ≥ 65 years]
- Age category at the start of treatment [<65 years, ≥ 65 to <70 years, ≥ 70 to <75 years, ≥ 75 to <80 years, ≥ 80 to <85 years, ≥ 85 years]
- Inpatient/outpatient status at the initial prescription [inpatient, outpatient]
- Height at the start of treatment (by sex) (continuous data)
- Body weight at the start of treatment (by sex) (continuous data)
- Body weight category at the start of treatment (by sex) [<40 kg, ≥ 40 to <50 kg, ≥ 50 to <60 kg, ≥ 60 kg]
- Name of target disease (i.e., diagnosis of neuropathic pain) [by disease name]
- Duration of target disease (i.e., diagnosis of neuropathic pain) (continuous data)
- Severity of target disease (i.e., diagnosis of neuropathic pain) [mild, moderate, severe]
- Pain score (continuous data)
- Name of underlying disease (i.e., primary disease of nerve damage that cause neuropathic pain) [by disease name]
- Hepatic impairment [no, yes (mild, moderate, severe)]
- Renal impairment [no, yes (mild, moderate, severe)]
- Hemodialysis [no, yes]
- Creatinine clearance category [<15 mL/min, ≥ 15 to <30 mL/min, ≥ 30 to <60 mL/min, ≥ 60 mL/min]
- Hyperalgesia [no, yes]
- Past medical history [no, yes]
- Complications [no, yes]

The following number and proportion of patients will be tabulated by SOC and PT in the safety analysis set.

- Breakdown of underlying disease
- Breakdown of past medical history
- Breakdown of complications

The following number and proportion of patients will be tabulated in the safety analysis set and efficacy analysis set.

- Presence or absence and breakdown of concomitant medications
- Presence or absence and breakdown of concomitant non-medication therapies
- Presence or absence and breakdown of prior medications

If patient demographics are tabulated by subgroup based on the initial dose specified in Section 5.4, the following will be tabulated in the safety analysis set and efficacy analysis set in accordance with Section 8.1.

- Age at the start of treatment (continuous data)

- Age category at the start of treatment [<15 years, ≥ 15 to <65 years, ≥ 65 years]

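### The primary efficacy measure (response rate) is compared between subgroups by unadjusted tests only, although baseline pain is collected and the pain-change analysis of the same factors adjusts for it.

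*SAP*

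**What the plan says.** - **Primary efficacy item.** Protocol 7.2.2: "In the efficacy analysis set, the response rate will be set as a primary analysis item". SAP 8.2.4.1 defines it: "Response rate (number of effective patients / [number of effective patients + number of ineffective patients]) and its 95% confidence interval will be calculated".
- **What is judged.** SAP 6.2 describes clinical efficacy as a comparison with the patient's own starting condition: "Efficacy of Lyrica at Week 13 will be assessed relative to baseline (including the day of start of treatment". Protocol 6.7 has the investigator enter effective, ineffective or impossible to judge.
- **Subgroup test for response.** SAP 8.2.4.6: "Tests specified in Section 8.1.3 will be performed to evaluate the relationship between patient demographics, etc. and clinical efficacy". Section 8.1.3 provides that Fisher's "exact test and Cochran-Armitage test (exact method) will be performed for the relationships with nominal scale data and ordinal scale data, respectively", plus risk ratio and risk difference with 95% intervals. It names no covariate, stratum or model.
- **Subgroup test for pain change.** For this outcome the next sentence of 8.2.4.6 turns to a model: "test based on the analysis of covariance model specified in Section 8.1.1 will be performed to evaluate the relationship between patient demographics, etc". Section 8.1.1 specifies that model as "using the factor to be evaluated as a factor and the value before administration as a covariate".
- **Baseline pain.** It is collected on a 0 to 10 scale before treatment (Protocol 6.5) and listed in the general demographics of SAP 8.2.2 as "Pain score (continuous data)". It is not among the 17 efficacy factors in SAP 5.4, and it is not in the separate list in 8.2.2 that describes the initial-dose groups.
- **Covariates.** SAP 6.4 states that none, actual or potential, have been identified for safety or efficacy.

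**The concern.** Finding factors that affect efficacy is one of the survey's stated aims (SAP 2.2), and a significant test in 8.2.4.6 leads to further tabulation by that factor. The comparison of the primary measure is crude, while the comparison of a further measure, on the same factors, is adjusted for the starting value.

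A judgement made relative to the starting condition may depend on how much pain there was to lose and on regression to the mean. If it does, and a factor's categories start at different pain levels, the crude comparison mixes the factor with starting pain. A factor with no effect could then be reported as affecting efficacy, or a real effect could be hidden. A factor might also be significant for response and null for pain change, and the plan offers no way to tell whether the endpoint or the adjustment explains the difference.

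**Working it through.** **1. The plan's own figures.** The SAP states no calculation for the efficacy subgroup tests. Its only design figures concern safety, and they reproduce: 1 − 0.999^3400 = 96.7% (stated as 97%). The exact lower limit for 380/5134 is 6.70%, and 0.0670 × 3400 = 227.8 (stated as 227 or more). Neither bears on this point.

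**2. Inputs.** From the documents: two-sided 5% level (SAP 4.1), target of 3400 patients (Protocol 3), pain scale 0 to 10 (Protocol 6.5), about 100 patients in each of six pain types (Protocol 3). Not in the documents, and therefore assumed: the response rate, the spread of baseline pain, the slope of response on baseline pain, and the baseline gap between subgroups.

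**3. Model.** logit P(effective) = a + b × (baseline pain − 6), with no factor term, so the true factor effect is zero. Each simulated survey is tested by Fisher (crude) and by logistic regression on factor plus baseline pain (adjusted).

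**4. Set A.** Two equal subgroups, 75% response at pain 6, SD 2, 1000 surveys per case. Slopes of −0.1 and −0.2 are odds ratios of exp(−0.1) = 0.90 and exp(−0.2) = 0.82 per point.

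| Slope b | Gap (points) | N=3400 crude / adjusted | N=1000 crude / adjusted |
|---|---|---|---|
| 0 | 1.0 | 4.8% / 6.1% | 4.1% / 5.0% |
| −0.2 | 0 | 4.7% / 5.2% | 4.4% / 4.7% |
| −0.1 | 0.5 | 7.9% / 5.0% | 4.3% / 4.3% |
| −0.1 | 1.0 | 18.5% / 3.8% | 8.8% / 5.0% |
| −0.2 | 0.5 | 20.3% / 5.6% | 9.3% / 5.5% |
| −0.2 | 1.0 | 67.0% / 4.6% | 25.5% / 4.1% |

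The spurious risk difference in the last four rows is 0.9 to 3.6 percentage points.

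Hand check of the largest case: the marginal response rates are 76.2% and 72.6%, a difference of 0.036. The standard error with 1700 per group is √[(0.762×0.238 + 0.726×0.274)/1700] = 0.0150, so z = 0.036/0.0150 = 2.4, and Φ(2.4 − 1.96) ≈ 0.67. This agrees with the simulation.

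**5. Set B, varying subgroup size.** N=3000, about 72% response, baseline pain with mean 6 and SD 2.2, odds ratio per point 1.2, 1.1 or 0.9.

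- Subgroup of 30% (900 patients), 1-point gap: crude rejection of about 42% to 46% (OR 1.2), 15% (OR 1.1) and 18% (OR 0.9). With a 0.5-point gap it is 5% to 14%. Adjusted rejection is 5% to 7%.
- Subgroup of 10% (300 patients), 1-point gap: 19%, 9% and 10%. With a 0.5-point gap it is 6% to 8%.
- Subgroup of 3% (90 patients): 5% to 8% with a 1-point gap, 5% to 6% with a 0.5-point gap.

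The spurious difference is about 3.4 points for OR 1.2, 1.7 for OR 1.1 and −1.9 for OR 0.9 with a 1-point gap. Its direction therefore depends on the sign of the slope, which is unknown.

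**6. Reading.** Both conditions are needed. With slope zero or gap zero, the crude test stays at or below 5%. Inflation is material for large splits of the full survey and small for pain types near 100 patients.

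**The case against.** The strongest case on the other side has five parts.

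- **Neither condition is documented.** A reader might infer that starting pain does distort the response comparisons. The documents do not support that. They give no baseline pain by subgroup and no relation between baseline pain and the effective/ineffective judgement, and SAP 6.4 reports no covariates. This stands, and it limits the point to what can happen.
- **The covariance model proves little about response.** A change score contains its own baseline, so adjusting for it is routine. Clinical efficacy is a global judgement that is not computed from the pain score. This stands: the asymmetry does not show that baseline pain is prognostic for response.
- **The large rejection rates need favourable inputs.** The 67% needs the steepest assumed slope, a full 1-point gap and two halves of 3400. This also stands.
- **Some comparisons are narrower than they look.** Initial-dose response rates are calculated in SAP 8.2.4.7 without a test. In Appendix A2.1, efficacy risk ratios are not planned for inpatient status, and none are planned for target disease. A reader should not infer that every subgroup carries a crude efficacy risk ratio.
- **There are safeguards.** Testing is exploratory (SAP 4.1) with no decision rule (4.2). The adjusted pain-change analysis runs on the same factors. Demographics may be tabulated for significant factors, and the initial-dose list includes disease severity. These soften the concern but do not close it. The label does not remove confounding from a reported risk ratio, and the covariance model has a different outcome. The tabulation is optional, adjusts nothing, and would not be triggered by a masked effect. Severity in three grades is coarse and is not used for adjustment.

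**Conclusion.** The point holds as a possibility that the plan leaves unexamined, not as a demonstrated bias. The primary efficacy measure is compared across the SAP 5.4 factors without adjustment, although a relevant baseline value is collected and is used as a covariate for pain change on those factors. Under the assumed inputs with no true factor effect, crude rejection ranges from about 4% to 67%, against about 4% to 7% after adjustment, and the spurious difference is about 1 to 4 percentage points. For subgroups of about 100 patients the inflation is slight.

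These sizes rest on the assumed response rate, spread, slope, gap and subgroup share. Baseline pain is also only one possible confounder, since each factor is tested singly. A supplementary analysis is proportionate: the measure is primary, finding factors is a stated aim, and no new data are needed.

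**What to change.** 1. In SAP 8.2.4.6, keep the exact tests and add a supplementary logistic or modified Poisson model of effective/ineffective with the 5.4 factor and baseline pain score (continuous), for factors whose categories are large enough to fit.
2. Report the adjusted risk ratio or risk difference with its 95% interval, beside the crude result, and the number of patients excluded for a missing baseline score.
3. Add baseline pain score to the initial-dose demographics list in SAP 8.2.2.
4. Reconcile SAP 6.4 (no covariates identified) with 8.1.1 (pre-treatment value used as covariate).
5. State that the 8.1.3 response comparisons are unadjusted and that all of these tests remain exploratory.

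The cost is SAP wording and one model per eligible factor. There are two drawbacks. Patients without a baseline score drop out of the adjusted model, so the adjusted and crude results may rest on different patients. Sparse categories, for example the youngest age group or the lowest creatinine clearance group, may not be estimable and would keep the exact test alone. Since the survey was already complete at SAP version 8.0, the model should be labelled as a later, supplementary addition.
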